2 DESCRIPTION OF OBJECTIVES AND ENDPOINTS

The objectives and endpoints of the study are listed below.

The secondary efficacy endpoints have been ranked based on the order of clinical importance.

Primary Objective	Primary Endpoints
To evaluate the clinical efficacy of BIIB054 via dose response using the change from baseline in Movement Disorder Society-Unified Parkinson's Disease Rating Scale (MDS-UPDRS) Total Score	Change from baseline in MDS-UPDRS Total Score (Sum of Parts I, II, and III) at the primary timepoints of Week 52 and Week 72
Secondary Objectives	Secondary Endpoints
To evaluate the clinical efficacy of BIIB054 based on MDS-UPDRS subparts	Change from baseline to Week 52 in MDS-UPDRS the subparts III, II and I (each part separately)
	Change from baseline to Week 72 and end of study in MDS-UPDRS the subparts III, II and I (each part separately)
To assess the PK profile of BIIB054	Concentration of BIIB054 in the serum
To evaluate the dose-related safety of BIIB054	Incidence of adverse events (AEs) and serious adverse events (SAEs)
To evaluate the pharmacodynamic effects of BIIB054 on the integrity of nigrostriatal dopaminergic nerve terminals	Change from baseline to Week 52 in striatal binding ratio (SBR) in the putamen, striatum, and caudate as measured by single-photon emission computed tomography (SPECT) imaging of the dopamine transporter (DaT) with ioflupane I123 (DaTscan™)

CONFIDENTIAL

The information contained herein may not be used, disclosed, or published without the written consent of Biogen MA Inc.

To evaluate the immunogenicity of BIIB054	Incidence and titer of anti-BIIB054 antibodies in the serum
Exploratory Objectives	Exploratory Endpoints

[Redacted]
	
[Redacted]
 
 • [Redacted] • [Redacted] • [Redacted] • [Redacted] • [Redacted] - [Redacted] - [Redacted] - [Redacted] • [Redacted]
	
[Redacted]

	[REDACTED]
	[REDACTED]
	[REDACTED] • [REDACTED] • [REDACTED]
	[REDACTED] • [REDACTED] • [REDACTED] • [REDACTED] [REDACTED] • [REDACTED] - [REDACTED] - [REDACTED]

[REDACTED]	[REDACTED]
[REDACTED]	[REDACTED]
[REDACTED]	[REDACTED]
[REDACTED]	[REDACTED]
[REDACTED]	[REDACTED]
[REDACTED]	[REDACTED]
[REDACTED]	[REDACTED]

CONFIDENTIAL

The information contained herein may not be used, disclosed, or published without the written consent of Biogen MA Inc.

[REDACTED]
	
[REDACTED]
 
• [REDACTED]• [REDACTED]• [REDACTED]• [REDACTED]• [REDACTED]

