3 STUDY DESIGN

3.1 Study Overview

This Phase 2a, randomized, double-blind, parallel-group, placebo-controlled study (Year 1) with an active-treatment dose-blinded period (Years 2 through 4) will examine the efficacy, safety, PK, and pharmacodynamics of BIIB054, administered every 4 weeks via IV infusion

CONFIDENTIAL

The information contained herein may not be used, disclosed, or published without the written consent of Biogen MA Inc.

to adult subjects with PD. Approximately 311 subjects will be enrolled at about 85 sites globally.

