3.1.1 Year 1 (Placebo-Controlled Portion of the Study)

Prior to the first dose in Year 1, all subjects in the study will be randomized into 4 arms, to receive 13 doses of BIIB054 (250, 1250, or 3500 mg) or placebo.

Subjects will be enrolled into 2 cohorts. Cohort A will be randomized first, in a 1:1:1:1 ratio into each of the 4 treatment arm and will include approximately 24 subjects. Randomization and dosing for Cohort B (approximately 287 planned subjects) will start after all subjects in Cohort A complete Week 12 assessments, and all available safety and PK data are reviewed by the IDMC. Randomization of subjects in Cohort B will be stratified by baseline (Day 1) MDS-UPDRS Part I + II + III total scores (≤ 35 and > 35) and striatum SBR (≤ 1.2 and > 1.2), and subjects will be randomized at Day 1 into 1 of 4 parallel dosing arms in each stratum.

After all subjects in Cohort A complete Week 12 assessments (28 days after their third infusion), and before dosing any subjects in Cohort B, all available safety and PK data will be reviewed by the IDMC. No subjects in Cohort B may be dosed until the IDMC review is complete. The study schematic is presented in [Figure 1](#). After IDMC review is complete, subjects in Cohort B will be randomized, and dosing may begin. During the review period, subjects in Cohort A will continue to be dosed on a schedule of once every 4 weeks.

The first IDMC meeting will occur after the last subject in Cohort A completes Week 12 assessments, or approximately 6 months after the first subject has been enrolled in Cohort A, whichever comes first. Regular IDMC meetings will occur approximately every 3 months after the first meeting.

[REDACTED]

The Week 48 infusion is the last infusion of the placebo-controlled period, and Week 52 is the first dosing of the Dose-blinded portion of the study.

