3.1.2 Years 2 Through 4 (Active-Treatment Dose-Blinded Portion of the Study)

Prior to Infusion 14 (the first dose of Year 2) at Week 52, subjects who received placebo in Year 1 will be randomized into 1 of the active-dosing arms for Year 2; these subjects will receive BIIB054 in Year 2. Subjects who received BIIB054 (1250 mg or 3500 mg) in Year 1 of the study will continue with the same dose regimen in Year 2. Subjects receiving the 250-mg dose in Year 1 continued on their original dose assignment.

Subjects will receive 12 additional doses of BIIB054 (250, 1250, or 3500 mg) in Year 2 and up to 16 additional doses in Years 3 and 4. Up until the last subject in the study has had his or her last dose in Year 2 of the study (Week 96 Visit), eligible subjects will be able to continue treatment once every 4 weeks.

Subjects who complete dosing through Week 96 and the Final Visit 12 weeks after the last visit will be considered Year 2 completers in the eCRF.

CONFIDENTIAL

[figure not shown]
The information contained herein may not be used, disclosed, or published without the written consent of Biogen MA Inc.

See Figure 2 for a depiction of the duration of dosing in Years 3 and 4 for subjects continuing dosing past Week 96.

Figure 4 on protocol presents a flowchart for dosing and procedures from Week 96 through end of study, including how to determine which subjects are eligible to continue dosing past Week 96.

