5.3.5 Assessment of the Impact of Covid-19 on the clinical outcome analyses

As this study is on-going when the Covid-19 public health emergency (PHE) occurred, subject visits and data collection were impacted, including missing visits, missed assessments, delayed visits and/or some visits were performed via remote assessments, e.g. telephone/video visits. Every effort was made to document these impacted study activities systematically on the eCRF and other electronic source data.

A complete listing of all visits impacted (e.g. missed visits, delayed or assessment done via remote visits) will be listed in the clinical study report.

In addition, subgroup analyses of the selected key clinical outcome MDS-UPDRS will be performed on a subset of subjects who did not have ≥ 3 consecutive missing doses throughout the study to further evaluate the impact of Covid-19 on the study. The same MMRM model for the primary analyses will be used for the subgroup analyses.

In addition, due to Covid-19, some visits were delayed. A few subjects will have their Week 52 imaging done at later visits up to Week 72 and these will still be considered as Week 52 visit data in the analyses for Week 52. These data were not included in the Week 52 database lock in time, but will be included in the Week 72 database, and the related Week 52 imaging analyses will be updated at the time of the Week 72 interim analyses.

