5.5.5 Analysis methods

The estimand of the primary analysis for imaging outcome measure is the mean difference of the change from baseline in the imaging measure at Week 52 between treatment groups in the

	Statistical Analysis Plan Placebo-Controlled Period	V1.0
---	---	-------------

pharmacodynamics population regardless of whether start of PD medication had occurred or not. Specifically, the estimand takes the following into consideration:

- A. Population: pharmacodynamics population as defined in Section 5.1.2;
- B. Variable: change from baseline to Week 52 in the imaging measure;
- C. Intercurrent events: regardless of whether start of PD medication had occurred or not;
- D. Population-level summary: difference in variable means between each active treatment and placebo group

A set of DaT/SPECT measures and [REDACTED] have been selected for the statistical analyses based on literature review and clinical inputs before the DBL. Please see Appendix VI for the listed measures.

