4.6.3 Additional analyses of placebo-controlled period due to COVID-19

Due to COVID-19 public health emergency, considerations were made to allow week 52 assessments to be delayed up to 4 weeks. If this occurs, some of the data may not be included in the all patient week 52 analyses, as they may miss the timeline of the corresponding

CONFIDENTIAL

The information contained herein may not be used, disclosed, or published without the written consent of Biogen MA Inc.

	Statistical Analysis Plan Dose Blinded Extension Period	V2.0
---	---	-------------

interim database lock. However, these data are still considered in the placebo-controlled period because they are before the first dose of DBE period. Depending how much data are missing in the all patient week 52 analyses database lock, the MMRM analyses in the placebo-controlled period may be repeated by including all the available data in the placebo-controlled period.

[REDACTED]

[REDACTED]

[REDACTED]

[REDACTED]

[REDACTED]

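### Imaging taken as late as Week 72 is filed as Week 52 data without requiring that the scan precede extension dosing, so drug-exposed scans can enter the placebo arm of the DaT/SPECT comparison

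*SAP*

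**What the plan says.** The affected endpoint is secondary: "Change from baseline to Week 52 in striatal binding ratio (SBR) in the putamen, striatum, and caudate" (Year 1 SAP, section 2). Its estimand is the "difference in variable means between each active treatment and placebo group" (Year 1 SAP 5.5.5). The only intercurrent event named there is the start of PD medication, and the only imaging sensitivity analysis (5.5.6) removes scans taken after PD medication.

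On the switch to active drug, Year 1 SAP 3.1.1 says "Week 52 is the first dosing of the Dose-blinded portion of the study", and 3.1.2 says "Prior to Infusion 14 (the first dose of Year 2) at Week 52, subjects who received placebo in Year 1 will be randomized" to one of the active arms. Infusions are "administered every 4 weeks via IV infusion" (3.1).

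On delayed scans there are three statements:

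- Year 1 SAP 5.3.5 describes, for a few subjects, "Week 52 imaging done at later visits up to Week 72 and these will still be considered as Week 52 visit data". These scans missed the Week 52 database lock, will be in the Week 72 database, and the Week 52 imaging analyses will then be updated.
- DBE SAP section 5 repeats this.
- DBE SAP 4.6.3 speaks of Week 52 assessments delayed by up to 4 weeks, some of which may miss the interim lock. It then says: "However, these data are still considered in the placebo-controlled period because they are before the first dose of DBE period". The placebo-controlled MMRM may be repeated with them.

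**The concern.** The Week 52 binding-ratio comparison is informative because the control arm has had no BIIB054. The rule in 5.3.5 does not protect that. A placebo subject who has begun extension infusions can supply a scan labelled placebo, Week 52, and the scan also carries up to 20 extra weeks of disease course. The imaging MMRM treats time as categorical, so a 72-week change enters as a 52-week change with no correction. Neither the estimand nor the planned sensitivity analysis covers the switch to active drug.

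The statements also give a programmer no single instruction. Section 4.6.3 rests on scans being taken before dosing, within a 4-week delay. Section 5 of the same SAP, like Year 1 SAP 5.3.5, allows 20 weeks and sets no such condition. Different Week 52 imaging datasets could each be defended from the text.

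**Working it through.** The plan gives no power or bias figure for this endpoint, so there is none to reproduce. The check is timeline arithmetic followed by a bounded dilution calculation.

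**Timeline.** Inputs: extension dosing starts at Week 52 (3.1.1, 3.1.2), the interval is 4 weeks (3.1), and the latest accepted scan is at Week 72 (5.3.5).

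- Extra time: 72 − 52 = 20 weeks, which is 20/52 = 38% more follow-up and 20/4 = 5 times the delay in DBE SAP 4.6.3.
- Infusions before a Week 72 scan in a switched placebo subject: Weeks 52, 56, 60, 64 and 68, so 5. There are 6 if the Week 72 infusion precedes the scan.

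**Dilution.** Set the true 52-week active-minus-placebo effect to 1. Let f be the share of placebo scans taken at Week 72. The plan gives no f, so 2% to 20% is an assumption. Of the 101 placebo subjects in Year 1 SAP Table 4.2, that is about 2 to 20. Lateness is taken as equal in all arms, so the untreated decline over the extra weeks cancels.

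- *Linear accrual in switched placebo subjects, no further gain in the active arms:* difference = 1 − f × 20/52.
- *Full catch-up by Week 72:* difference = 1 − f.
- *Purely linear slope effect in all arms:* active = (1 − f) + f × 72/52, placebo = f × 20/52, so difference = 1 − f + f × 52/52 = 1.

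| f | Approx. n of 101 | Shrinkage, linear accrual | Shrinkage, full catch-up | Shrinkage, purely linear slope |
|---|---|---|---|---|
| 2% | 2 | 0.8% | 2% | 0 |
| 5% | 5 | 1.9% | 5% | 0 |
| 10% | 10 | 3.8% | 10% | 0 |
| 20% | 20 | 7.7% | 20% | 0 |

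**Unequal lateness.** Let d be the difference between arms in the share of late scans, and r the fraction of decline that the drug prevents. A late scan on drug has declined by a further (1 − r) × 20/52 of the untreated 52-week change. The spurious difference, as a share of the true effect, is d × (1 − r) × (20/52) / r. With d = 5 percentage points:

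- r = 50%: 0.05 × 0.5 × 0.385 / 0.5 = 1.9%.
- r = 25%: 0.05 × 0.75 × 0.385 / 0.25 = 5.8%.

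The sign depends on which arm has more late scans. Both d and r are assumed.

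**The case against.** The strongest reply is that an analysis without these scans already exists. Year 1 SAP 5.3.5 says they missed the Week 52 lock, so the full 1-year analysis in section 6 runs first without them, and results before and after the update can be compared. The same section promises a listing of delayed visits in the study report. This stands and lowers the stakes. It does not settle which version is definitive, and the wording about updating suggests that the later one replaces the first.

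A second reply is that extension dosing may have been held until the late scan. Section 5.3.5 neither says nor requires this, and the visit-window appendix is a separate document that is not shown. What is established is a missing condition. A reader might infer that contamination has occurred, but the documents do not show that.

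A reader might also infer that the two SAPs contradict each other, with the DBE SAP imposing a rule that scans precede the first extension dose. They do not differ in that way: both carry the Week 72 rule, and 4.6.3 gives the timing as a reason for keeping data delayed up to 4 weeks, attached to an optional re-analysis. The conflict is between 4.6.3 and the Week 72 rule, and so lies partly within the DBE SAP.

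**Conclusion.** The concern holds as a gap in a data-inclusion rule for a secondary endpoint, and it should be fixed. As written, the updated Week 52 DaT/SPECT analysis can include placebo-arm scans taken after about five BIIB054 infusions, and nothing in the estimand or the planned sensitivity analysis addresses this.

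The likely effect is small. The text speaks of a few subjects, which points to the low end of the assumed 2% to 20% range. Exposure in the placebo arm pulls the difference towards zero. Only unequal lateness between arms could create a spurious difference, and the documents indicate none.

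A reader might take 20/52 = 38% as the size of the bias. It is an upper bound for a single scan at exactly Week 72 under linear decline; the contrast between arms moves far less, or not at all under a linear slope with equal lateness. Nor does the point reach the primary MDS-UPDRS analysis or its alpha allocation. The imaging endpoint carries no multiplicity control.

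**What to change.** Put one identical rule in Year 1 SAP 5.3.5 and DBE SAP 4.6.3 and section 5. In the definitive Week 52 DaT/SPECT comparison with placebo, a delayed scan counts as Week 52 only if it was taken before that subject's first extension dose. The condition should apply to every arm, and the text should name which Week 52 imaging analysis is definitive.

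Treat later scans as missing at Week 52 in the planned MMRM, which already assumes data missing at random. List them by arm with their timing, and report the analysis that includes them as a sensitivity analysis only.

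Moving late scans to their actual time would not fit the planned model: time is categorical, and the key imaging visits in DBE SAP 4.6.2 are Weeks 24, 52, 96 and 148. If the midpoint windows stated for laboratory data in DBE SAP 4.5.3.1 also applied to imaging (an assumption), the boundary would be (52 + 96)/2 = Week 74, and a Week 72 scan would map back to Week 52. An explicit dosing condition is therefore needed.

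The cost is a wording change, a few lost Week 52 values and slightly less precision.

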5.4 Safety Analysis

5.4.1 General Considerations

Analysis population

All safety endpoints will be evaluated in the safety population (all subjects dosed) as defined in Section 5.1.2.

Methods of analysis

All adverse events (AEs) and serious adverse events (SAEs), clinical laboratory abnormalities, vital sign measurements, physical and neurological examination findings, 12-lead ECG readings, disease activity by brain MRI metrics, body weight and Columbia Suicide Severity Rating Scale (C-SSRS) will be evaluated for safety. Safety data collected by EOS defined in Section 5.1.1 will be used for the safety analyses. The main safety analysis will include data after PD medication. Additional analyses may be performed by excluding

CONFIDENTIAL

The information contained herein may not be used, disclosed, or published without the written consent of Biogen MA Inc.

data after PD medication. Unless mentioned otherwise, all safety data will be summarized by treatment group and overall active group.

Although treatment assignment error is not expected, if some subjects received different study treatment than the randomization allocation, the safety analyses will be based on the actual treatment allocation. Specifically, if a subject who was assigned placebo received BIIB054 at any visit at the same dose level by mistake, this subject will be included in the BIIB054 group of that dose in the safety statistical analyses; if a subject was assigned placebo or BIIB054 of certain dose level, but received BIIB054 at multiple dose level by mistake, this subject will be included in the BIIB054 group of the dose level that were taken the most frequently in the safety statistical analyses; on the other hand, if a subject who was assigned BIIB054 does receive placebo by mistake, this subject will be included under placebo group in the safety statistical analyses only when this subject received placebo at all study visits.

For the clinical laboratory assessments, vital sign measurements and 12-lead ECG readings, subjects in Cohort A have additional post-baseline visits between Day 1 and Week 12, comparing to Cohort B. The summary of numerical changes over time, i.e., the quantitative analysis will be based on the pooled data of both Cohort A and Cohort B and the common visits. All the qualitative analyses including the shift analysis, grade analysis and so on will be based on all the data of Cohort A and Cohort B of all visits. All the listings will be based on all the data of Cohort A and Cohort B of all visits.

Visit windows for mapping safety endpoint

For safety data that are summarized by visit, assessment from all scheduled visits, EOT visit, EOS visit and unscheduled visits will be mapped to an appropriate analysis visit using a windowing scheme (Appendix II).

5.4.2 Clinical Adverse Events

For this study, any AE experienced by a subject between the time of first dose of study treatment (Day 1/Baseline) and the end of study visit is to be recorded on the CRF, regardless of the severity of the event or its relationship to study treatment. Any SAE experienced by the subject between the time the subject has signed the ICF and the end of study visit is to be recorded, regardless of the severity of the event or its relationship to study treatment.

All AEs will be coded using the MedDRA and will be analyzed based on the principle of treatment emergence. An AE will be regarded as treatment-emergent if it was present prior to the first dose and subsequently worsened in severity or was not present prior to first dose but subsequently appeared.

In order to define treatment emergence for AE with missing start or stop dates, the following additional criteria will be used:

- If both the start and stop dates for a particular event are missing, then that event is considered treatment-emergent;
- If the start date for a particular event is missing and the stop date/time falls after the first dose date/time, then that event is considered treatment-emergent;

CONFIDENTIAL

The information contained herein may not be used, disclosed, or published without the written consent of Biogen MA Inc.

- If the start date is the same as the first dose date, and the start time is missing, then that event is considered treatment-emergent.

For events with a partial start date, the year/month of the event date will be compared to that of the first dosing date to determine whether the event is treatment emergent.

Only TEAEs and TESAEs will be summarized in the tables, unless otherwise specified. All SAEs (including pre-dosing SAEs) will be included in the listing of SAEs, with an indicator of pre-dosing or treatment-emergent. Only TEAEs will be included in other AE listings, if not otherwise specified.

The overall summary table of AEs will present the number of subjects with the following events for each treatment group, BIIB054 total and overall. A subject is counted only once in each category.

- Any AE;
- AE by severity as measured in CTCAE grade of version 5.0: 1 (mild), 2 (moderate), 3 (severe or medically significant), 4 (life-threatening), 5 (death)
- Study drug-related AE;
- [REDACTED];
- Radioligand related AE;
- Any SAE;
- Study drug-related SAE;
- [REDACTED];
- Radioligand related SAE;
- AE leading to discontinuation of study treatment; and
- AEs leading to withdrawal from study
- Death

The incidence of AEs will be summarized using the primary system organ class (SOC) or preferred term (PT) or both, sorted by decreasing frequency and alphabetical order, respectively. Additionally, AEs at least 5% higher in incidence for any active group compared to placebo group will be summarized by SOC and PT.

The incidence of AEs will also be summarized by severity as measured in CTCAE grade of version 5.0 using system organ class and preferred term. Within each system organ class or/and preferred term, the same subject will be counted only once. Under the same system organ class or/and preferred term, the occurrence of the adverse event with the greatest severity will be used in the calculation of incidence by severity.

The study drug related AEs, [REDACTED] and radioligand related AEs will be summarized by SOC, PT and treatment group as well.

The incidence of SAEs will be summarized by primary system organ class, preferred term and treatment group. Study drug related SAEs, [REDACTED] and radioligand related SAEs will be summarized in the same fashion as well.

Tables of AEs that led to study drug discontinuation and AEs that led to study withdrawal by SOC, PT and treatment group will be presented.

CONFIDENTIAL

The information contained herein may not be used, disclosed, or published without the written consent of Biogen MA Inc.

Listings of all AEs, SAEs, AEs that led to study drug discontinuation, and AEs that led to study withdrawal will be presented. Listing of death will be provided if applicable.

In some AE/SAE listings, complete AE start and end dates are needed to calculate the relative study days of AE start and end. Therefore, any partial date will be imputed for these listings. Specifically, the partial AE start date will be imputed as the earliest possible date on or after the first dose based on the partial information, and the partial AE end date will be imputed as the latest possible date on or before the EOS.

AEs around the time of infusion

The incidence of AEs within 2 hours from infusion start will be summarized by preferred term and visit for each treatment group. At each visit, the same subject will be counted only once within each preferred term. Preferred terms will be ordered by decreasing frequency of AEs in the BIIB054 total column. Listings of such AEs within 2 hours from infusion start will be provided by treatment group.

